6 CLINICAL SUPPLIES

Commercially available *Dysport* will be used in the study but will not be supplied by the study Sponsor per the non-interventional nature of the study.

6.1 Clinical Supply Identification and Use

Dysport is a white lyophilised powder provided in a vial containing 300 U botulinum toxin type A hemagglutinin complex, 125 µg human serum albumin, and 2.5 mg of lactose. Each vial will be reconstituted with 0.9% sodium chloride for injection to yield a solution containing 200 U per mL. A total volume of 0.25 mL of reconstituted *Dysport* will be administered in 5 equal aliquots of 0.05 mL each.

The product should be stored at the recommended temperature (between 2°C and 8°C). The product does not contain any antimicrobial agent. Therefore, it is recommended that the product is used immediately after reconstitution. It should not be frozen and should be protected from light.

6.1.1 Product Description

Table 3 Description and Usage of the Study Drug

	Product
Trade Name	Dysport
Name of Drug Substance	abobotulinumtoxinA
Internal Code	N/A
Pharmaceutical Form	Lyophilised powder
Strength	300 U per vial
Packaging	Single-use vial for reconstitution with 1.5 mL 0.9% Sodium Chloride Injection
Storage conditions	2-8°C
Reconstitution volume	1.5 mL
Dosage	50 U total (0.25 mL total) 10 U per injection site (0.05 mL per injection site)
Route	Intramuscular injection
Dose regimen	Up to three treatment cycles, 3-6 months apart
Location of treated area	Glabellar region

6.1.2 Subject Identification Number (SIN)

Each study participant who has signed the ICF will be entered into the electronic Case Report Forms (eCRF) system and a subject number will be assigned via the eCRF system. Subject numbers will consist of the study center number followed by a consecutive number starting with 001 at each center. The subject numbers shall be allocated in ascending sequential order within each center. The reason for excluding a consenting subject from entering the study should be specified in each case. A screen failure should not be re-screened in the study.

All subjects who have signed the ICF should be listed. Sufficient information to link the eCRF to the medical records should be recorded in the source documentation.

For the duration of the entire study, the subject will be identified using the subject number for all documentation and discussion.

6.1.3 Method of Treatment Assignment

Not applicable; this is a non-interventional study.

6.1.4 Randomization Number

Not applicable; this is a non-interventional study.

6.1.5 Dosage and Administration

This is a non-interventional study. The decision by the physician to treat the subject with *Dysport* on a long term bases must be made before including the subject in the study. The physician is free to choose *Dysport* modalities of administration in accordance with the approved leaflet in China.⁴

The units of Botulinum Toxin Type A are specific to the preparation and are not interchangeable with other preparations of botulinum toxin.

Botulinum Toxin Type A must be administered by appropriately qualified physicians with relevant professional knowledge and skills.

When preparing and handling Botulinum Toxin Type A solutions, the use of gloves is recommended. If Botulinum Toxin Type A dry powder or reconstituted solution should come into contact with the skin or mucous membranes, they should be washed thoroughly with water.

Dysport is supplied as a single-use vial. Each vial is intended for one treatment administration session for a single subject. When reconstituting the product, the exposed central portion of the rubber stopper should be cleaned with alcohol immediately prior to piercing the septum. A sterile 23 gauge (G) or 25 G needle should be used. The product should be reconstituted with 1.5 mL of sodium chloride injection (0.9%) to yield a solution containing 200 U per mL. Appearance of product after reconstitution: A clear, colorless solution, free from particulate matter.

Prior to injection, remove any make-up and disinfect the skin with a local antiseptic.

Before injection, place the thumb or index finger firmly below the orbital rim in order to prevent extravasation below the orbital rim. The needle should be pointed upward and medially during the injection.

[figure not shown]
In order to reduce the complication of ptosis, the following steps should be taken:

- Avoid injections near the *levator palpebrae superioris* muscle, particularly in patients with larger *depressor supercilii*.

- Injections in the *corrugator* muscle must be made into the central part of that muscle, at least 1 cm above the orbital rim.

The recommended dose is 50 U (0.25 mL of reconstituted solution) of *Dysport* divided into five injection sites, 10 U (0.05 mL of reconstituted solution) administered intramuscularly, at right angles to the skin, into each of the five sites: two injections into each *corrugator* muscle and one into the *procerus* muscle near the nasofrontal angle as shown in [Figure 2](#). Intramuscular injections performed with a sterile 29-30 G needle.

Figure 2 Injection Sites for Treating Glabellar Lines

1. Procerus 2. Corrugator 3. Lateral Corrugator/Orbicularis

Immediately after treatment of the patient, any residual *Dysport* which may be present in either vial or syringe should be inactivated with dilute hypochlorite solution (1% available chlorine).

Spillage of *Dysport* should be wiped up with an absorbent cloth soaked in dilute hypochlorite solution.

Any unused product or waste material should be disposed of in accordance with local requirements.

Discard needle and syringe in accordance with local regulations.

6.1.5.1 *Post-treatment Care*

Subjects should be provided with post-treatment care instructions per the physician's real clinical practice.

6.1.5.2 **Treatment Regimen**

The treatment regimen will be performed according to the approved leaflet in China and the physician's real clinical practice. Each enrolled subject will receive treatment with *Dysport* in the GL at Visits 1, 3, and 5, scheduled three to six months apart.

6.2 **Product Packaging and Labeling**

Commercially available *Dysport* will be used in the study.

6.3 **Supplies Management**

6.3.1 **Accountability**

Commercially available *Dysport* will be used in the study. The physician is responsible for supplying the product used in the study, and accountability should be documented according to the physician's real clinical practice.

6.3.2 **Storage of Study Drug(s)**

Dysport should be stored in accordance with the approved leaflet in China.

6.3.3 **Dispensing and Return**

Not applicable; this is a non-interventional study.

6.3.4 **Treatment Compliance Management and Record**

This is a non-interventional study. The decision by the physician to treat the subject with *Dysport* on a long term bases must be made before including the subject in the study. The physician is free to choose *Dysport* modalities of administration in accordance with the approved leaflet in China.

The treatment is an injection administered by the physician. Injection practice details for each injection visit, including muscle(s) injected, total dose and volume, dose and volume per injection point, and number of injection points will be collected per the study objectives.

6.3.5 **Product Quality Complaints**

Product Quality Complaints (PQCs) should be reported to **CCI** [REDACTED] A PQC is an external judgement presuming a quality defect of a product; quality issue for a product relating to its presentation or use, identified by a subject, a practitioner, physician, or study center personnel, a distributor, or anyone else involved in clinical supplies handling. Examples may include but are not limited to appearance issues, odor, damaged stoppers, low fills, and foreign matter in the product. These complaints may or may not represent a potential risk to the subject. A PQC should be clearly

2021-06-28 08:30

Effective date:

described in an email submitted by the study center personnel to **CCI** [REDACTED] within 24 hours of awareness. Affected study product should be quarantined, and not used, until further notice by the **CCI** [REDACTED]

CCI [REDACTED] [REDACTED] [REDACTED]

See [Investigator and Administrative Structure](#) for additional contact details.

In addition to submitting the PQC, any subject reaction associated with a PQC should be documented and evaluated by the physician according to [Section 8](#).

6.4 Dose Modification

Per real clinical practice, the physician is to administration *Dysport* in accordance with the approved leaflet in China.⁴

6.5 Blinding

Not applicable; this is a non-interventional study.

Effective

2.0

7 EFFICACY ASSESSMENTS

7.1 Subject Satisfaction Questionnaire

Subjects will be asked to complete the Subject Satisfaction Questionnaire, all or in part as specified, at all study visits, prior to treatment, as applicable ([Appendix 1](#)). The subject should complete the questionnaire independent of the physician.

7.2 Physician Satisfaction Questionnaire

Physicians will complete the Physician Satisfaction Questionnaire, all or in part as specified, at all study visits, prior to treatment, as applicable ([Appendix 2](#)). The physician should complete the questionnaire independent of the subject.

7.3 Subject Self-Assessment of GL Severity

Subjects will evaluate the appearance of their glabellar lines at max frown using a 4-point Categorical Scale. The 4-point Categorical Scale represents the severity of glabellar lines from no wrinkles (grade 0) to severe wrinkles (grade 3) as represented in [Table 4](#).

The subject self-assessment of GL severity will be complete at all study visits, prior to treatment, as applicable, and should be made independently of the physician's assessment. See [Appendix 3](#) for additional details and subject instructions.

Table 4 4-point Categorical Scale of GL Severity

Grade	Severity of Glabellar Lines
0	No wrinkles
1	Mild wrinkles
2	Moderate wrinkles
3	Severe wrinkles

With guidance from the physician, subjects may also reference the [CCI](#) when completing their self-assessment.

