Exclusion Criteria	
 1. Hypersensitive to Dysport or its excipients. 2. Presence of contraindications to Dysport treatment as specified in the approved leaflet in China. 3. Subject is at risk for precautions, warnings, and/or contraindications to Dysport as specified in the approved leaflet in China 4. Subject has an infection in the proposed treatment area. 5. Subjects has had treatment failure experience with other toxins. 6. Pregnant or breast feeding female, or female intending to get pregnant during the study. 7. Participation in a clinical study, interventional or non-interventional, within 30 days prior to study entry (signature of informed consent). 	
Treatment:	
This is a non-interventional study (NIS). The decision by the physician to treat the subject with Dysport on a long term basis must be made before including the subject in the study, and has to be clearly separated and independent of the decision to include the subject in the study.
 
Commercially available Dysport will be used in the study but will not be supplied by the study Sponsor. The physician is free to choose Dysport modalities of administration in accordance with the local SmPC and the approved leaflet in China.
	

Effective date: 2021-06-28 08:30

Effective

2.0

		
	
Product: Commercially available Dysport, a BoNT-A product.
 
Strength/Concentration: 300 units (U) per vial
 
Reconstitution Volume: 1.5 milliliter (mL)
 
Dosage (total dose per treatment): 50 U total (0.25 mL total) 10 U per injection site (0.05 mL per injection site)
 
Route: Intramuscular injection
 
Treatment Regimen: Three injection cycles, 3-6 months apart
 
Location of Treated Area: Glabellar region
	
	
Efficacy Assessments: Efficacy assessments include:
 
 • Subject Satisfaction Questionnaire • Subject assessment of GL severity at max frown using the 4-point Categorical Scale • Physician Satisfaction Questionnaire • Physician assessment of GL severity at rest and max frown using the Investigator's 4-point Photographic Scale • Injection practice details 	

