3 OVERALL CLINICAL STUDY DESCRIPTION

This is a prospective, longitudinal, non-interventional, multi-center study to collect subject and physician satisfaction, and treatment experience with *Dysport* in real clinical practice in subjects of Chinese origin.

Approximately 250 subjects are planned to be included in the study to receive three injection cycles with *Dysport* in the GL. The decision by the physician to treat the subject with *Dysport* on a long term basis must be made before including the subject in the study, and has to be clearly separated and independent of the decision to include the subject in the study.

Given the non-interventional nature of the study, subject visits, treatment regimen, and the administration of *Dysport* to treat GL will be carried out according to the physician's real clinical practice and the approved leaflet in China.

The study consists of three injection cycles. Each injection cycle includes an injection visit and a follow up visit three weeks later (\pm 7 days). Following the 1st injection at Visit 1, subsequent injections, i.e., 2nd injection and 3rd injection, will be scheduled three to six months apart. The final follow up visit will be held three to six months after the subject's 3rd injection.

The screening visit and the 1st injection visit may be conducted on the same day. Data will be collected at all visits, if held. Subjects and physicians, independent of each other, will assess the subject's GL severity, and will complete a questionnaire about satisfaction with treatment outcomes at all visits.

Injection practice details for each injection visit, including muscle(s) injected, total dose and volume, dose and volume per injection point, and number of injection points will be collected per the study objectives.

Adverse events (AEs) will be collected during the study.

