Appendix 3 Subject Self-Assessment of GL Severity using the 4-point Categorical Scale

Subject#:

Visit #:

Date of completion (DD/MM/YYYY):

Subject Instructions: Using a mirror, evaluate your ‘glabellar lines’ (the lines between your eyebrows) while you are frowning. To produce a ‘max frown’ you are to raise your eyebrows, then bring them together as strongly as you can. You may repeat this until you are comfortable with frowning. Evaluate your lines at max frown according to these four categories shown below.

These assessments will be repeated at each visit in the study center and we will ask that you make the max frown in exactly the same way on each occasion. Please place a mark (X) in the box that best describes how you think the lines between your eyebrows look when frowning today.

At max frown:

No wrinkles (smooth skin)	Mild wrinkles (fairly smooth skin)	Moderate wrinkles (glabellar lines)	Severe wrinkles (severe glabellar lines)

Please be advised that you will be using the same scale to rate the appearance of your glabellar lines at every visit.

Note: The subject should perform their self-assessment independently of the physician’s assessment.

Note: With guidance from the physician, subjects may also reference the **CCI**
CCI when completing their self-assessment.

Effective

Effective date: 2021-06-28 08:30

2.0

Effective

Effective date: 2021-06-28 08:30

CCI

2.0

Effective date: 2021-06-28 08:30

Investigator's Validated 4-point Photographic Scale

[figure not shown]
At Rest

Characterized by muscle activity at the time of evaluation having limited impact on their presence or absence

GRADE 2: MODERATE / 中度

GRADE 3: SEVERE / 重度

PPD

Dermal crease – A deep linear depression in the skin surface that is deeper and/or wider than a fine wrinkle distinguishable from a dermal groove by the absence of muscle contractions at rest.

Dermal groove – A deep linear depression in the skin surface distinguishable from a dermal crease by the presence of persistent muscle contraction or spasm visible when the patient is "at rest".

Effective

2.0

Effective date: 2021-06-28 08:30

Investigator's Validated 4-point Photographic Scale

At Max Frown

Glabellar lines produced by maximal voluntary muscular activity contributing to the presence of the lines

GRADE 0: NONE / 无

GRADE 1: MILD / 轻度

PPD

Relaxed skin tension line; no wrinkles

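### Subject severity grades are meant to be independent of the physician's, yet the physician may guide subjects through an optional second aid while they rate, so anchors can vary and grades can be steered

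*Protocol*

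**What the plan says.** The independence requirement appears at two strengths in the protocol.

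- **Wider.** The Synopsis (Clinical Study Design) and Section 3 use the same sentence: "Subjects and physicians, independent of each other, will assess" the severity of the subject's lines at all visits.
- **Narrower.** Section 7.3 says the self-rating "should be made independently of the physician's assessment". The note on the subject's form in Appendix 3 repeats this: "The subject should perform their self-assessment independently of" the physician's assessment.

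The allowance for the aid follows in the same two places. Section 7.3 and the next note in Appendix 3 both say "With guidance from the physician, subjects may also reference the" a further aid (name redacted) when completing the self-assessment.

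The recording scale is fixed: "Subjects will evaluate the appearance of their glabellar lines at max frown using a 4-point Categorical Scale". The Synopsis lists this rating among the efficacy assessments: "Subject assessment of GL severity at max frown using the 4-point Categorical Scale".

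**The concern.** An independent self-rating is useful because it offers a second view of the outcome from someone other than the treating physician. Here the physician may take part while the subject is choosing a grade. That physician also grades the same lines at maximum frown (Section 7.4) and gives the injection (Section 9.1.2), and there is no blinding (Section 6.5). From Visit 2 onward the physician has already graded that subject at least once.

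Two things are at stake. First, guidance can move a subject's grade toward the physician's view without the physician's grade ever being disclosed. Agreement between the two ratings would then be partly built in. Second, use of the aid is optional, so some ratings rest on four verbal categories and others on those categories plus a guided reference. If use differs between the 10 planned centres, or between visits for one subject, differences in subject severity can arise that have nothing to do with treatment.

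**Working it through.** No arithmetic applies. The plan gives no figure on this point, and the concern does not depend on sample size, error rate or power. The check sets the relevant sections side by side.

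1. **Is guidance given during the rating or beforehand?** Section 7.3 and Appendix 3 both place it at the time the subject completes the self-assessment. It is not described as prior training.

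2. **Is it limited?** The visible text does not say what guidance may cover. It neither restricts it to explaining a sheet nor excludes help with choosing a grade.

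3. **Is use of the aid uniform?** The wording is permissive. The visible text does not say when the aid is to be used, whether its use must be the same across visits and centres, or whether it is recorded. Table 2 schedules the subject's rating at all seven visits, so the choice can recur seven times per subject.

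4. **Does the instrument change?** No. Section 7.3 gives one scale, grades 0 to 3. Sections 9.1.3 and 9.1.4 add the word static to its name but refer to the same Section 7.3 and Appendix 3. Appendix 3 tells subjects that the same scale applies at every visit. What can change is the anchor behind the four boxes.

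5. **What is the aid?** Its name is redacted. The only other severity scale shown in the protocol is the investigator's photographic scale, which the Synopsis assigns to the physician's rating. That makes it the likely aid, but this is an inference.

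6. **In what order are the ratings made?** In Section 9.1.2 the subject's rating is step 2 and the physician's is step 4. In Sections 9.1.3 and 9.1.4 they are steps 1 and 3. The subject goes first on paper at every visit, but no section states that the order is binding.

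7. **Which analyses use the rating?** The primary endpoint is Question 17 of the Subject Satisfaction Questionnaire at Visit 6 (Protocol 2.1.1, SAP 4.1.1), on a separate form. The visible secondary endpoints (SAP 4.1.2 and 7.4.2) also come from the satisfaction questionnaires. Parts of both lists are redacted, so the endpoint role of subject severity cannot be seen. No subject–physician agreement analysis is visible.

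Steps 1 to 3 establish the problem; steps 4 to 7 limit it.

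**The case against.** The strongest reply is that Section 7.3 does not contradict itself. It asks for independence from the physician's assessment, that is, from the physician's grade. Explaining how to use a reference aid does not reveal that grade. Where the protocol wants independence from the physician as a person, it says so: Section 7.1 does this for the Subject Satisfaction Questionnaire. The listed visit order also puts the subject's rating first, and limits on guidance may sit in redacted text.

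Much of this stands. A reader might infer a flat contradiction within Section 7.3, but its narrower wording does not support that. The tension is with the wider wording in the Synopsis and Section 3, which covers the severity ratings expressly. A listed order also does not stop guidance from shaping a grade before the physician records one. What the redactions hide is unknown, so the point rests only on the visible sentences.

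A reader might also infer that subjects rate with different instruments. The documents do not support this: the aid is an additional reference, and every grade goes into the same four boxes. Nor can one state as fact that the aid is the photographic scale.

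Finally, it can be said that the harm is conjectural. It is true that nothing shows steering will occur. The point is that the written procedure allows it, and the visible text does not provide for showing afterwards where it happened.

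**Conclusion.** The concern holds in a limited form. The protocol promises severity ratings made independently by subject and physician. It then allows the treating, unblinded co-rater to guide an optional aid while the subject rates. The likely effects are uneven anchoring across subjects, visits and centres, and some pull of subject grades toward the physician's.

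The size cannot be derived. A figure for inflated agreement would need the agreement expected without guidance and the share of subjects who take over the physician's view; the documents give neither, so no number is offered.

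A reader might infer that the main result of the study is compromised. It is not: the primary endpoint uses a separate questionnaire, and SAP Section 5 sets no hypothesis. The conclusion assumes only that guidance may go beyond handing over the aid, which the visible wording permits. It does not depend on what the aid is. This is a cheap improvement, not a condition for the study's validity.

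**What to change.** Revise Section 7.3 and the Appendix 3 note in the same terms:

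- Set one rule for the aid for all subjects at all visits: either it is never used, or the same printed sheet is always provided.
- State that the physician gives no help in choosing a grade.
- Make the order already listed in Sections 9.1.2 to 9.1.4 binding, so that the subject's grade is completed before the physician's is recorded or disclosed.

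The cost is wording. If the aid is withdrawn, subjects lose an optional help.

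If ratings have already been collected under the present text, state in the study report that the aid was optional and could be used with physician guidance. Treat this as a limitation of the subject severity data, and do not present subject–physician agreement as independent confirmation.
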